#### **4.5.4.2 Part 2: Chronic Hepatitis B Patients**

No specific food is prohibited in this study.

Dosing with RO7020531 or placebo will be given in fasted state (at least 2 hours after a meal or 2 hours before the next meal), in Cohorts 1, 2 and 3 together with the patient's NUC treatment.

Alcohol consumption is to be strongly discouraged. During the study, patients should consume no more than an average of 20 g of alcohol daily. Please refer to [Appendix 7](#) for the calculation of alcohol standard drinks as relates to eligibility criteria. Patients will be queried on a regular basis about their alcohol consumption and appropriate comments concerning this intake will be recorded on the eCRF.

### **4.6 STUDY ASSESSMENTS**

#### **4.6.1 Description of Study Assessments**

All examinations listed below will be performed according to the Schedule of Assessments (SoA) outlined in [Appendix 1](#).

At time-points when several pre-dose assessments coincide, the following sequence should be followed:

- Urine collection (urinalysis, urine PK pre-dose sample).
- ECG recordings.
- Vital signs.
- Pre-dose blood sampling (pre-dose PK, pre-dose PD, HBV assessments, exploratory samples, safety blood tests).
- RO7020531/placebo and NUC intake.

For the post-dose assessments, the following sequence should be followed with the PK blood sample (or PD blood sample if there is no PK sampling) to be taken at the nominal time-point:

- ECG recordings.
- Vital signs.
- Post-dose blood sampling (post-dose PK, post-dose PD).

#### **4.6.1.1 Medical History and Demographic Data**

Medical history includes clinically significant diseases, surgeries, reproductive status, smoking history, use of alcohol and drugs of abuse.

In addition, for Part 2, medical history includes detailed HBV history: date of HBV diagnosis, mode of HBV transmission, HBV genotype (if documented), all previous HBV treatments, occurrence of NUC analogue resistance (if any), previous evaluations for cirrhosis, dates/outcomes of liver biopsies (if any).

Previous treatments include all medications (e.g., prescription drugs, over-the-counter drugs, herbal or homeopathic remedies, vitamins, nutritional supplements) used by the HV/patient within 4 weeks prior to the screening visit.

Demographic data will include age, sex, and self-reported race, ethnicity and origin (origin will be collected for Asian subjects only).

#### **4.6.1.2 Physical Examinations**

A complete physical examination should be performed at time-points indicated in the SoA ([Appendix 1](#)) and includes an evaluation of the head, eyes, ears, nose, throat, neck and lymph nodes, and the cardiovascular, dermatological, musculo-skeletal, respiratory, GI and neurological systems. A genitourinary examination may be performed in case of evocative symptoms at the Investigator's discretion. Any abnormality identified at screening or at baseline should be recorded on the Medical History eCRF.

For patients in Part 2, during the treatment period, a basic and/or symptoms-directed physical examination (at least lungs, cardiovascular, abdomen, extremities, lymph nodes) should be performed according to the SoA ([Appendix 1](#)). No recording of weight is required during these basic/symptoms-directed physical exams.

Targeted or symptoms/AE-directed physical examinations should be performed if needed at all other visits at the discretion of the Investigator.

Clinically significant changes from a baseline abnormality showing its improvement or resolution should be recorded on the Additional Observation eCRF. New or worsened clinically significant abnormalities should be recorded as AE on the AE eCRF ([Section 5.3.5](#)).

Height will only be recorded at screening. Weight will be recorded at time-points for complete Physical Examination as specified in the SoA ([Appendix 1](#)). BMI will be calculated at screening in accordance with the formula provided in [Appendix 2](#).

#### **4.6.1.3 Vital Signs**

Blood pressure (BP), pulse rate, respiratory rate and body temperature will be recorded at the time-points specified in the SoA ([Appendix 1](#)).

Blood pressure, respiratory rate and pulse rate should be obtained in a quiet room at a comfortable temperature, with the HV/patient's arm unconstrained by clothing or other material. Blood pressure, respiratory rate and pulse rate will be obtained after the HV/patient has been in a supine or sitting position for at least 5 minutes. All blood pressure and pulse rate measurements will be obtained from the same arm (where possible), in the same position and, with the same cuff size, using an automatic instrument with a digital readout, throughout the study. Body temperature measurement can be either oral or tympanic; the method should be maintained throughout the study.

Blood pressure measurement will be performed in triplicate (can be as short as 20 second to 1 minute interval between measurements). The mean of three consecutive replicates will be used as the value for the defined time-point.

#### **4.6.1.4 Electrocardiograms**

Triplicate 12-lead ECG recordings (i.e., three useful ECGs without artifacts) will be obtained within approximately 2-5 minutes at each specified time-point. The average of the three readings will be used to determine ECG intervals (PR [PQ], QRS, QT, QTcF). The intervals will be captured or calculated, and the changes in T-wave and U-wave morphology will be documented. T-wave information will be captured as normal or abnormal, U-wave information will be captured in two categories: absent/normal or abnormal.

Whenever possible, the same brand/model of a standard digital high-quality, high-fidelity electrocardiograph machine equipped with computer-based interval measurements should be used for each HV/patient. The conditions should be as close as possible to pre-dose time-points; this includes but is not limited to food intake, activity level, stressors and room temperature.

To minimize variability, it is important that HV/patients be in a resting position for  $\geq 10$  minutes prior to each ECG evaluation. Body position should be consistently maintained for each ECG evaluation to prevent changes in heart rate. Environmental distractions (e.g., television, radio, conversation) should be avoided during the pre-ECG resting period and during ECG recording. ECGs should be performed prior to any scheduled vital sign measurements and blood draws. In some cases, it may be appropriate to repeat abnormal ECGs to rule out improper lead placement as contributing to the ECG abnormality.

For safety monitoring purposes, the investigator must review, sign and date all ECG tracings. Paper copies will be kept at the study centers with the HV's/patient's clinical file as part of the permanent record. The ECG intervals and interpretation will be recorded on the eCRF or may be sent electronically. If considered appropriate by Roche, ECGs may be analyzed retrospectively at a central laboratory.

If any ECG recording documents QT/QTc values  $> 500$  msec or increases from Day -1 QTc  $> 60$  msec (as provided by the machine), the site should repeat the ECG triplicate within the next 5 minutes and notify the Sponsor. If confirmed, ECG recordings should be repeated at least hourly until two successive ECGs show QTc values below the threshold value that triggered the repeated measurement.

#### **4.6.1.5 Laboratory Assessments**

Normal ranges for the study laboratory parameters must be supplied to the Sponsor before the study starts. Laboratory safety tests shall be collected at time-points specified in the SoA ([Appendix 1](#)). Results of clinical laboratory testing will be recorded on the eCRF or will be received as electronically produced laboratory reports submitted directly from the local or central laboratory.

Additional blood or urine samples may be taken at the discretion of the Investigator if the results of any test fall outside the reference ranges, or clinical symptoms necessitate additional testing to monitor HV's/patients' safety. In the event of unexplained abnormal clinically significant laboratory test values, the tests should be repeated immediately and followed up until the values have returned to the normal range and/or an adequate explanation of the abnormality is found.

In Part 2 Cohorts 1, 2 and 3, only a central laboratory will be used; however, unscheduled local laboratory tests may be ordered per Investigator discretion. In this case, a duplicate sample should simultaneously be sent to the central laboratory for analysis.

In Part 2 Cohort 4 at the Day -1 (baseline) visit, a duplicate sample will be taken for liver function tests (ALT) and sent to central laboratory and local laboratory. The local laboratory sample is required to confirm eligibility for liver function parameters before dosing a patient on Day 1. The local laboratory result will not be used for statistical analysis. In the rare event that a patient is deemed to be eligible for the study based on the results of the local test, but the central laboratory test results (conducted after the patient has been dosed) differ, the patient should continue on the study.

At screening, where the clinical significance of abnormal laboratory results is considered uncertain, lab tests may be repeated before randomization to confirm eligibility. If a HV/patient fails an inclusion/exclusion criterion due to a transient and non-clinically significant condition at screening, the Investigator may repeat the relevant screening assessment(s) within the 28-day screening period. If there is an alternative explanation for a positive urine test for drugs of abuse, e.g., previous occasional intake of a medication or food containing for example codeine, benzodiazepines or opiates, the test should be repeated to confirm washout. Please see Section 4.6.2.1 for details on re-screening in Part 2.

For more details on unscheduled laboratory tests see Section 4.6.2.4.

For sampling procedures, storage conditions, and shipment instructions, see the separate laboratory manual.

For safety outcome measures see Section 3.3.1.

Based on the ongoing data review, any sample type not considered to be critical for safety may be stopped at any time if the data from the samples collected does not produce useful information.

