#### **4.2.2.2 Part 2: Chronic Hepatitis B Patients**

Patients must meet the following criteria for study entry:

1. Adult male and female patients, 18 to 65 years of age, inclusive.
2. Informed of, and willing and able to comply with, all of the protocol requirements and the investigational nature of the study, and have signed an informed consent form (ICF) in accordance with institutional and regulatory requirements.
3. A BMI between 21 to 32 kg/m^2, inclusive. Male patients must be above 55 kg and female patients above 45 kg body weight.
4. CHB infection (positive test for HBsAg for more than 6 months prior to randomization).

5. For Cohort 1, 2, 3 and 4: HBsAg detectable at screening.
6. For Cohort 1, 2 and 3: On treatment with tenofovir, entecavir, adefovir, or telbivudine, either as single agents or in combination, for at least 6 months.  
For Cohort 4: HBV treatment naïve or not on any anti-HBV treatment for the past 6 months.
7. For Cohort 1, 2 and 3: HBV DNA < 90 IU/mL for at least 6 months prior to randomization; HBV DNA < 90 IU/mL at screening by Roche Cobas assay.  
For Cohort 4: HBV DNA at screening  $\geq 2 \times 10^4$  IU/mL for HBeAg positive and  $\geq 2 \times 10^3$  IU/mL for HBeAg negative patients.
8. For Cohort 1, 2 and 3: Alanine amino transferase (ALT)  $\leq 1.5 \times$  upper limit of normal (ULN) during the 6 months prior to randomization confirmed by two measurements separated by at least 14 days (one of the ALT measurements can be done at screening); ALT at screening  $\leq 1.5 \times$  ULN.  
For Cohort 4: ALT and aspartate aminotransferase (AST) at screening and Day -1 visit:  $\leq 5 \times$  ULN.
9. Screening laboratory values (including hematology, chemistry, urinalysis) obtained up to 28 days prior to first study treatment within acceptable range or judged to be not clinically significant by the Principal Investigator (PI) and Medical Monitor.
10. Gamma glutamyl transpeptidase (GGT), alkaline phosphatase (ALP), albumin, total and direct bilirubin within normal range or judged to be not clinically significant by the Investigator and Medical Monitor at screening.
11. Negative ANA test, or positive with dilutions not greater than 1:40 and with no associated history or symptoms of potential connective tissue disease or other immune-mediated diseases.

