### **Screening and Safety Samples**

Samples for the following blood and urine laboratory tests will be sent to one or several local laboratories (Part 1 only) or central laboratories or to the Sponsor for analysis. Urine dipstick tests will be done locally by the sites for Part 1 and Part 2. Instruction manuals and supply kits will be provided for all laboratory assessments.

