#### **For Part 1 and Part 2**

- Hematology: Hemoglobin (Hb), hematocrit, total WBC count, differential WBC count (including basophils, eosinophils, lymphocytes, monocytes and neutrophils), platelet count, red blood cells count (RBC), mean corpuscular volume (MCV), mean corpuscular hemoglobin (MCH), mean corpuscular hemoglobin concentration (MCHC) and reticulocyte (%) counts.
- Coagulation: PT, INR, and aPTT.
- Blood Chemistry: ALT, AST, total and indirect bilirubin, ALP, GGT (only at screening), total protein, albumin, urea, creatinine, uric acid, total cholesterol, triglycerides, glucose, sodium, chloride, potassium, calcium, phosphorus, bicarbonate, cystatin C, HbA1c (only at screening).
- Urinalysis: A midstream, clean-catch urine specimen will be collected for dipstick analysis of protein, blood, glucose, leucocytes and pH. If the dipstick result is 2+ or greater for blood, protein or leucocytes, urine will be sent to the laboratory for microscopy. If there is an explanation for the positive dipstick result, e.g., menses, it should be recorded, and there is no need to perform microscopy.

- Pregnancy Test: Serum or plasma beta-human chorionic gonadotropin ( $\beta$ -HCG) at screening, urine on all other occasions (females only).
- Substance use: Drugs of abuse urine test and alcohol test (only at screening and Day -1). A breath test may be used to test for alcohol.
- Viral Serology:
  - Part 1 (only at screening): Hepatitis A (IgM anti-HAV), Hepatitis B (HBsAg), HCV, HIV.
  - Part 2: Viral screening tests (HAV, HCV, Hepatitis D, HEV, HIV). For HBV assessments and schedule see Section 4.6.1.8 (HBV-Specific Viral Assessments) and SoA ([Appendix 1](#)).
- Hormones (only at screening): Follicle-stimulating hormone (females only to confirm post-menopausal status).
- Thyroid Function Tests (only at screening): TSH, free T3 and free T4.
- Autoimmune Panel (only at screening): ANA, AMA, ASMA and thyroid peroxidase antibody.

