## **Appendix 1 Schedule of Assessments: CHB Patients Who Are Not on Antiviral Treatment (Part 2 Cohort 4) Detailed**

- a) Vital signs include blood pressure, pulse rate, respiratory rate and body temperature (oral or tympanic). Blood pressure, respiratory rate and pulse rate will be obtained after the patient has been in a supine *or sitting* position for at least 5 minutes.
- b) 12-lead ECGs will be obtained in triplicate (three consecutive interpretable 12-lead ECGs within a 2–5 minute interval) after the subject has been in a supine position for at least 10 minutes. Automated ECG intervals (PR (PQ), QRS, QT, QTcF) and HR will be captured or calculated, and the changes in T-wave and U-wave morphology will be documented.
- c) Plasma PK samples for RO will be collected pre dose and 0.25, 1, 2, 4, 6, 8 and 24 hours post-dose on Day 1 of Week 1 and on Day 41. PK samples will be collected pre-dose and 2-4 hours post-dose on Days 3, 5, 7, and 21.
- d) During treatment period, blood samples for protein biomarkers and RNA will be collected 6, 8 and 24 hours post-dose on Day 1; pre-dose *and 4–6 hours post-dose on Day 3 and Day 5; pre-dose, 4–6 hours and 24 hours post-dose on Day 7 and Day 21; and pre-dose, 6 and 24 hours post-dose on Day 41.*
- e) Blood for RBR DNA sample will be collected on Day 1 from all patients who signed RBR ICF. If, however, the RBR DNA blood sample is not collected during the scheduled visit, it may be collected at any time during the conduct of the clinical study.
- f) If the clinical genotyping blood sample is not collected at Day 1, it may be collected at any time during the conduct of the clinical study.
- g) A duplicate sample will be taken for liver function tests (ALT) and sent to the central laboratory and local laboratory. The local laboratory sample is required to confirm eligibility for liver function parameters before dosing a patient on Day 1. If the patient is deemed to be eligible for the study based on the results of the local test, but the central laboratory test results differ, the patient should continue on the study.
- h) Optionally, the safety monitoring after dosing on Day 3 and Day 5 can be extended to 12 hours in patients who develop flu-like symptoms/pyrexia and do not respond to symptomatic treatment at the Investigator's discretion
- i) Visits Day 15, 28 and 35 have a window of  $\pm 2$  days.
- j) Visits Day 21/22 can be also conducted on Day 19/20 or Day 23/24.

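### Cohort 4 eligibility requires AST as well as ALT at Day -1, but the local pre-dose sample is specified for ALT only, so Day -1 AST has no scheduled result before the first dose

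*Combined protocol and SAP*

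**What the plan says.** **The criterion.** Section 4.2.2.2, criterion 8, sets the transaminase limit for untreated patients: "For Cohort 4: ALT and aspartate aminotransferase (AST) at screening and Day -1 visit" must each be no more than 5 x ULN. The Synopsis gives the same criterion.

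**The pre-dose check.** Section 4.6.1.5 states that at the Cohort 4 Day -1 visit "a duplicate sample will be taken for liver function tests (ALT) and sent to central laboratory and local laboratory". Footnote g of the detailed Cohort 4 schedule repeats it: "A duplicate sample will be taken for liver function tests (ALT) and sent to the central laboratory and local laboratory". Section 4.6.1.5 gives the purpose of the local sample: "The local laboratory sample is required to confirm eligibility for liver function parameters before dosing a patient on Day 1".

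**The central result.** The same section covers a patient found eligible on the local test: "but the central laboratory test results (conducted after the patient has been dosed) differ, the patient should continue on the study".

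**Where AST is measured.** AST belongs to the blood chemistry panel listed in Section 4.6.1.5, and the Cohort 4 schedule collects that panel on Day -1. The general text on screening and safety samples says these tests "will be sent to one or several local laboratories (Part 1 only) or central laboratories or to the Sponsor for analysis".

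**The concern.** The local duplicate lets liver eligibility be confirmed before dosing, which the central Day -1 result, available only afterwards, cannot do. That reason applies to AST as much as to ALT, because criterion 8 treats the two alike. Yet both places that describe the duplicate name ALT alone. A site that follows the text will order local ALT and proceed to dosing without a Day -1 AST result.

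What is at stake is a stated liver entry criterion in the cohort that is not on antiviral treatment. There are two practical effects:

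- A patient can be dosed while failing half of the Day -1 criterion, which creates an eligibility deviation that the procedure itself allowed.
- That patient's AST baseline may be elevated. This matters for reading later values, because one of the Cohort 4 liver-event definitions in Section 5.3.5.6 compares ALT or AST both with 5 x ULN and with twice baseline.

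**Working it through.** The plan gives no figure to reproduce here. The check sets the provisions side by side.

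**1. What must be known before dosing, and what is scheduled**

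| Item | ALT | AST |
|---|---|---|
| Limit at screening (criterion 8) | 5 x ULN | 5 x ULN |
| Screening result reviewed before Day -1 (Section 4.6.2.1) | yes | yes |
| Limit at Day -1 (criterion 8) | 5 x ULN | 5 x ULN |
| Named on the local Day -1 duplicate (Section 4.6.1.5; footnote g) | yes | no |
| Central Day -1 result available before dosing (Section 4.6.1.5) | no | no |

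The Day -1 criterion needs two analytes and the scheduled pre-dose check supplies one. Footnote e of the Cohort 4 schedule nevertheless requires eligibility to be confirmed by Day -1.

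**2. Which patients the gap can reach**

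Take a patient who passed both limits at screening and consider Day -1:

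| Day -1 ALT | Day -1 AST | Meets criterion 8 | Outcome of local ALT check |
|---|---|---|---|
| at or below 5 x ULN | at or below 5 x ULN | yes | passes, correctly |
| above 5 x ULN | any | no | fails, correctly |
| at or below 5 x ULN | above 5 x ULN | no | passes, wrongly |

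Only the third row is affected. Screening runs from Day -28 to Day -2, so AST would have to rise above the limit within four weeks at most while ALT stays within it. The documents give no rate for this.

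**3. What happens to a patient in the third row**

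The continuation rule applies when the central result differs from the local one on which eligibility was based. With no local AST, the central AST has nothing to differ from, so the rule does not clearly cover this patient. No other provision addresses the case.

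**4. What an elevated AST baseline does**

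The combined transaminase and bilirubin definition for Cohort 4 in Section 5.3.5.6 asks for a treatment-emergent value above 5 x ULN and twice baseline. A patient whose AST baseline exceeds 5 x ULN already passes the absolute part. For AST to qualify, it would then have to rise beyond 2 x 5 = 10 x ULN. ALT could still meet the definition separately.

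**The case against.** The strongest reply is that AST was always intended. The duplicate is described with a plural, tests, and its purpose is to confirm eligibility for liver parameters, also plural. ALT and AST are the only liver parameters with a numeric Day -1 limit for Cohort 4, so the bracketed ALT may be loose shorthand. The statement that local laboratories are for Part 1 only does not settle the matter, since Section 4.6.1.5 already departs from it for Cohort 4, and the separate laboratory manual is not available here. This makes the intention uncertain. It does not remove the mismatch: both descriptions name ALT alone, and no text schedules a local AST.

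Three further points stand and limit the concern:

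- Screening AST is still reviewed against the same limit before Day -1.
- Section 4.6.2.4 lets an investigator order an unscheduled local test. A reader might infer that the AST half of the criterion cannot be applied at all. That goes too far; the result is not scheduled, but it can be obtained at discretion.
- A reader might also infer that a patient with a high central AST is kept in the study by rule. The documents do not say so, because the continuation rule addresses only disagreement between a local and a central result.

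The consequence for the analysis is also modest. Section 6 plans no formal hypothesis testing, and Section 6.4.1 includes every dosed patient in the safety population. The central Day -1 AST is still collected, so an elevated baseline would be visible. The transaminase limits named for discontinuation in Section 4.7.1.1 use ALT, which is checked locally.

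**Conclusion.** The plan is internally inconsistent and wrong as written on this point. Cohort 4 criterion 8 has a Day -1 AST limit for which no pre-dose result is scheduled, and a site following Section 4.6.1.5 and footnote g could dose a patient who fails it. This rests on reading the bracketed ALT as the list of analytes for the local duplicate, which is what both places state.

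The size of the problem cannot be derived from the documents. Section 1.2.2 reports 9 Cohort 4 patients dosed by 01 May 2020 and the cohort may reach 15, so at most 15 - 9 = 6 further patients would go through the procedure after that date. A reader might take those 6 as affected, or treat one patient's share of the active arm as the size of the problem. Neither is supported: the first counts patients who pass through the check, and the second assumes that a case occurs and is on active drug. Only patients whose AST passed at screening and exceeds the limit at Day -1 with local ALT within it are affected, and their number is unknown and may be zero.

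The expected consequence is avoidable eligibility deviations and possibly an elevated AST baseline in a small cohort. The planned descriptive summaries would change little. The correction is worth making because the conflict is between two explicit rules and is cheap to remove.

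**What to change.** Reconcile criterion 8 (Synopsis and Section 4.2.2.2) with Section 4.6.1.5 and footnote g of the detailed Cohort 4 schedule, so that the analytes in the Day -1 criterion are those on the local pre-dose sample. One way is to name AST together with ALT in Section 4.6.1.5 and footnote g. Which analytes govern Day -1 eligibility is for the sponsor to decide; the texts need to agree.

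In the same edit, state which analytes the continuation rule covers when the central Day -1 result becomes available, so that a central AST above the limit is not left unaddressed.

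Naming AST adds one analyte to a local sample that is already planned, with no extra visit or procedure. The laboratory manual should be checked for consistency with the revised text.
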